5 STUDY POPULATION

5.1 INCLUSION CRITERIA

All participants must meet the following inclusion criteria:

1. Adults, 18 to 80 years of age

[figure not shown]
2. Meets diagnostic criteria for isolated CD (idiopathic; dystonic symptoms localized to the head, neck, shoulder areas) with at least moderate severity at Baseline (Day 1), defined as a TWSTRS-total score of at least 20, with at least 15 on the TWSTRS-Severity subscale, at least 3 on the TWSTRS-Disability subscale, and at least 1 on the TWSTRS-Pain subscale (minimum TWSTRS subscale criteria applicable only to subjects not previously enrolled in Study Protocol 1720302)
3. Subjects who were previously enrolled in Study Protocol 1720302, who completed the study, including:
 - a) Those with no reduction or have an increase from baseline in the average TWSTRS-total score at Weeks 4 and 6 (i.e., no improvement or worsened disease status), and the investigator agreed that there was a need for retreatment based on the subject's symptoms and neurologic examination findings
 - b) Those who benefited from study treatment and complete follow-up study visits up to the time point of when their TWSTRS-total score reached/exceeded their target TWSTRS score
 - c) Those who benefit from study treatment but subsequently experienced significant recurrence of CD symptoms (e.g., pain) during the study before their TWSTRS-total score reached their target TWSTRS score and requested retreatment, which the investigator determined was warranted due based on the subject's symptoms and neurologic examination findings
 - d) Those who completed study visits up to Week 36 and their TWSTRS-total score never reached their target TWSTRS score and they never requested another treatment. The investigator determined that these subjects can be followed in the OLS until their TWSTRS-total score is the same or higher than their target TWSTRS score or until they request retreatment, which the investigator determined is clinically indicated
4. De novo subjects (not previously enrolled in Study Protocol 1720302):
 - a) Naïve to BoNT treatment
 - b) BoNT treatment-experienced; if previously treated with BoNTA, the subject must have demonstrated a clinically meaningful response to the last BoNTA treatment based on the clinical judgment of the investigator
5. Written informed consent including authorization to release health information

[figure not shown]

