9.6 PLANNED ANALYSES

All efficacy endpoints, including responder rates, will be summarized with descriptive statistics by dose and/or treatment cycle, unless otherwise specified.

Discontinuation rate will be summarized by dose and cycle as well as overall. Additionally, the number of weeks on study will be summarized with descriptive statistics.

Duration of effect after each treatment, defined as time (number of weeks) from treatment until loss of 80% of the peak treatment effect (i.e., the average of the change from baseline in the TWSTRS-total score at Weeks 4 and 6)

[figure not shown]
- If a subject has no reduction in the TWSTRS-total score at Week 4 and Week 6, his/her duration of effect will be set to 0. If a subject discontinues or withdraws from the study prior or at Week 6, his/her duration of effect will be set to 0.
- If a subject discontinues or withdraws from the study prior to reaching his/her target TWSTRS score at any visit after Week 6, his/her duration of effect will be censored at the last visit. If a subject rolled over from Study Protocol 1720302 at Week 36 prior to reaching his/her target TWSTRS score, his/her duration will be calculated from the injection date in Study Protocol 1720302 to the time his/her TWSTRS-total score reaches/exceeds the target TWSTRS score.

Kaplan-Meier survival curves will be plotted for each dose level for the time-to-event endpoints. Point estimate of median duration and 2-sided, 95% confidence intervals (CIs), will be generated using the log-rank test. A subject might be counted more than once or in multiple groups due to multiple injections cycle. Exploratory statistical comparisons between subgroups and duration of response evaluation may be performed.

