3.4. Brief Description

This is a Phase 3, open-label, multi-center trial to evaluate the long-term safety, efficacy, and immunogenicity of up to four continuous treatment cycles of DAXI for injection at doses of 125 U, 200 U, 250 U, and 300 U in adults with isolated CD at study centers across the United States, Canada, and Europe.

Approximately 350 adult subjects will be recruited from study centers who were previously enrolled in Protocol 1720302 entitled [A Phase 3, Randomized, Double-Blind, Placebo-Controlled, Parallel Group, Multi-Center Trial to Evaluate the Efficacy and Safety of a Single Treatment of DaxibotulinumtoxinA for Injection in Adults with Isolated Cervical Dystonia (ASPEN-1)]. These subjects will have 7 days from their End-of-Study (EOS) Visit in Protocol 1720302 to decide if they want to enroll in this study. After enrolling, subjects will have up to 21 days to complete screening procedures. After 21 days, subjects who have NOT completed the screening procedures will be considered a screen failure. To be reconsidered for enrollment to this study, the subject will be required to repeat all screening procedures to reconfirm eligibility for enrollment. These criteria also apply to subjects who missed the 7-day decision-making window to enroll in this study. This study will also recruit new botulinum neurotoxin (BoNT) treatment-naïve or -experienced adult subjects who were not enrolled in Protocol 1720302.

[REDACTED]

[REDACTED]

This document is confidential.

[REDACTED]

The primary endpoints are safety and immunogenicity. [REDACTED]

[REDACTED]

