7.5.2. Concomitant Medication

Medications that were taken on or after the first study medication dose date will be classified as concomitant. This classification includes medications that were started after the first study medication dose date or medications that began before and continued to be taken after the first study medication dose date.

[figure not shown]
This document is confidential.

8. Efficacy

[figure not shown]
All efficacy analyses will be performed for the safety population. Efficacy endpoints, including responder rates, will be summarized with descriptive statistics by dose and treatment cycle, unless otherwise specified.

[figure not shown]
This document is confidential.

[figure not shown]
This document is confidential.

[figure not shown]
This document is confidential.

[figure not shown]
This document is confidential.

This document is confidential.

This document is confidential.

This document is confidential.

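### Only Week 36 rollovers are timed from their Study 1720302 injection; if those durations join the by-dose curves from time 0, duration of effect is biased upward

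*Protocol*

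**What the plan says.** Protocol 9.6 defines the endpoint as "Duration of effect after each treatment, defined as time (number of weeks) from treatment until loss of 80% of the peak treatment effect", with the target TWSTRS score marking the event. It then makes one exception. "If a subject rolled over from Study Protocol 1720302 at Week 36 prior to reaching his/her target TWSTRS score", the clock starts at the earlier injection: "his/her duration will be calculated from the injection date in Study Protocol 1720302 to the time his/her TWSTRS-total score reaches/exceeds the target". The paragraph that follows states that "Kaplan-Meier survival curves will be plotted for each dose level for the time-to-event endpoints", with a median and a 2-sided 95% confidence interval.

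The exception covers the subjects of inclusion criterion 3d (Protocol 5.1): "Those who completed study visits up to Week 36 and their TWSTRS-total score never reached their target TWSTRS score". The other rollover groups are 3a (no improvement at Weeks 4 and 6), 3b ("Those who benefited from study treatment and complete follow-up study visits up to the time point of when their TWSTRS-total score reached/exceeded their target") and 3c (early symptom recurrence with a retreatment request).

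SAP 3.4 gives the title of Study 1720302 as a "Randomized, Double-Blind, Placebo-Controlled, Parallel Group, Multi-Center Trial to Evaluate the Efficacy and Safety of a Single Treatment". SAP Section 8 states that "All efficacy analyses will be performed for the safety population". SAP Section 10 drops the intent-to-treat and per-protocol populations and multiple imputation. Its visible text does not mention the Week 36 rule.

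**The concern.** Whether a Study 1720302 duration is counted depends on how long it lasted. A rollover still below target at Week 36 contributes one. Rollovers whose effect was absent (3a), ended earlier (3b) or was cut short by retreatment (3c) contribute none under any visible rule. Only the long tail is imported.

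This is left truncation with time counted from before entry. A 3d subject could not have been observed in this study with an event before Week 36, so those 36 weeks are immortal. In a Kaplan-Meier estimate without delayed entry, the subject sits in the denominator of every risk set before Week 36 and cannot contribute to the numerator.

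At stake is the reported durability of effect by dose. The imported injection's place is also undefined: the visible text does not say which dose level or cycle it belongs to, how placebo recipients of Study 1720302 are treated, or whether 3d subjects never re-dosed in the open-label study are counted.

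**Working it through.** The documents give no median duration, event count or number of Week 36 rollovers, so there is no figure of the plan to reproduce. The check is therefore a closed form for the direction, with assumed distributions for the size.

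**Inputs from the documents.** Time origin, event and by-dose Kaplan-Meier curves (Protocol 9.6). Event-free to Week 36 (Protocol 5.1, criterion 3d). Open-label follow-up of 52 weeks (Protocol 8.1.2.4). About 350 rollovers (Protocol 4.1).

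**Assumptions.** Weibull durations with true median 16, 20 or 24 weeks and shape 1 to 2; as a second model, lognormal durations with log-SD 0.5. Let f be the share of durations on a curve that come from Week 36 rollovers.

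**Direction.** Let S0(t) be the true curve. For t < 36 the imported durations contain no events, so the naive curve is

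S(t) = (1 − f)·S0(t) + f,

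which lies above S0(t) for any f > 0. This needs no distributional assumption.

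**Median.** Setting S(t) = 0.5 gives S0(t) = (0.5 − f)/(1 − f). Example, Weibull, median 20, shape 1.5, f = 10%: (0.5 − 0.1)/(1 − 0.1) = 0.444, and t = 20 × (−ln 0.444 / ln 2)^(1/1.5) = 20 × 1.170^(0.667) = 22.2 weeks.

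| Model, true median 20 | f | Naive median (weeks) |
|---|---|---|
| Weibull, shape 1.5 | 2% | 20.4 |
| Weibull, shape 1.5 | 5% | 21.0 |
| Weibull, shape 1.5 | 10% | 22.2 |
| Weibull, shape 1.5 | 20% | 25.2 |
| Lognormal, 10 added to 250 | 10/260 = 3.8% | 20.5 |
| Lognormal, 20 added to 250 | 20/270 = 7.4% | 21.0 |
| Lognormal, 40 added to 250 | 40/290 = 13.8% | 22.1 |

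The 250 is arbitrary; only the share matters. Over all the Weibull settings (medians 16 to 24, shapes 1 to 2), the shift is at most 0.7 week at f = 2%, 0.6 to 1.9 at 5%, 1.3 to 4.1 at 10% and 3.0 to 10.0 at 20%.

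**Proportion beyond 36 weeks.** The naive value is (1 − f)·S0(36) + f. Weibull, median 20, shape 1.5: S0(36) = 0.188, so at f = 10% it is 0.9 × 0.188 + 0.1 = 0.269. Lognormal, median 20: 12% becomes about 15%, 18–19% and 24% at the three shares above.

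**Simulation** (200 runs; 350 open-label durations censored at 52 weeks; Week 36 rollovers censored at 36 + 52 = 88 weeks; Weibull, median 20, shape 1.5):

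| f | Naive median | Delayed entry | Excluded | S(36) naive | S(36) delayed entry |
|---|---|---|---|---|---|
| 5% | 21.1 | 20.0 | 20.0 | 0.229 | 0.189 |
| 10% | 22.2 | 20.0 | 20.0 | 0.268 | 0.187 |
| 20% | 25.3 | 19.9 | 19.9 | 0.352 | 0.190 |

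Delayed entry at Week 36, or exclusion, removes the bias.

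**How many such subjects are plausible.** If all 350 rollovers had received DAXI and followed the lognormal model, the expected number event-free at Week 36 is 350 × 0.120 = 42 with a 20-week median and 350 × 0.052 = 18 with a 16-week median. Placebo recipients would change these counts, and repeat cycles on the same curve would lower f.

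**The case against.** *Pooling is inferred.* Protocol 9.6 says how one subject's duration is calculated, not that it joins the open-label curves. The rule may be meant only to complete the duration of the Study 1720302 injection, for which that injection date is the right origin. This stands in part. But the rule sits within the definition of the endpoint that the Kaplan-Meier paragraph goes on to plot, and no separate display is stated. Timing from that injection would be unbiased if all DAXI durations of Study 1720302 were included, and no visible text says so.

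*Redaction.* The SAP's detailed efficacy sections and parts of Protocol Section 9 are blacked out and could contain delayed entry, a dose assignment or a separate table. This stands, and it limits confidence. The silence of the visible part of SAP Section 10 does not show that the rule survived unchanged.

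*Placebo.* A reader might infer that placebo injections will be plotted as DAXI durations. The documents do not support that. Curves are by dose level, and a placebo injection has no DAXI dose level. The text is only silent on such subjects.

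*Subjects never re-dosed.* A reader might infer that SAP Section 8 drops them. SAP 5.3 requires enrolment and at least one dose of study drug, without saying that the dose must be given in the open-label study. The reading is plausible but not stated. If it is right, fewer imported durations remain, though each still exceeds 36 weeks.

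*Size.* A reader might infer a very large tail effect, for example 5% rising to 18% beyond 36 weeks with a true 16-week median. That takes 40 imported durations against 250, whereas the same model yields about 18 among 350 rollovers, giving (0.052 × 250 + 18)/268, or about 12%. In the 20-week lognormal case, 40 would be nearly all of the expected 42.

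**Conclusion.** The concern holds with moderate confidence on the visible text. Week 36 rollovers are the only subjects timed from Study 1720302, and they are event-free to Week 36 by selection. If their durations enter the by-dose curves from time 0, the bias before Week 36 is upward for any non-zero share. That direction needs no assumption about the distribution, but it does depend on pooling, which the text implies without stating.

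The size cannot be fixed from the documents. With an assumed true median of 20 weeks, the median shift is minor at a share of about 2% and material from about 10%. The tail beyond Week 36 is affected more.

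A reader might go further and conclude that the trial's main result is compromised. The documents do not support this: the primary endpoints are drug-related adverse events, discontinuations due to them, and immunogenicity, while duration is descriptive and any comparison exploratory. The point should be fixed before the duration analysis is run, but it does not threaten the primary objectives.

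**What to change.** Amend the SAP's duration definition as follows.

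- Start every duration on the open-label curves at an injection given in the open-label study.
- Report the Study 1720302 durations of Week 36 rollovers in a separate display. If they are kept on a curve, enter them at risk at Week 36 (delayed entry), limit them to DAXI recipients, and assign them to the dose received in Study 1720302.
- State whether 3d subjects never re-dosed in the open-label study are included in that display.
- Give the number of such subjects by dose, so that a reader can judge their weight.

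If the redacted SAP text already does this, a clarification that it supersedes the rule in Protocol 9.6 is enough.

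The cost is SAP wording, a little extra programming, and the treatment assignment and injection date from Study 1720302. No new data collection is needed. The downside is a slightly less favourable descriptive duration. Rebuilding the full Study 1720302 curve by randomized arm would also be unbiased, but it depends on that trial's analysis plan, which is not available here, so it is not a requirement of this fix.

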8.1.2.4 END-OF-STUDY VISIT

The EOS Visit for each subject in the OLS may occur when the subject:

- Prematurely withdraws from the study for specific reasons (e.g., AEs, pregnancy, or withdraws consent)
- Has no improvement or worsened disease status (i.e., lack of efficacy) after a treatment (consistent with no change or increase from baseline in the average of the TWSTRS-total score at Weeks 4 and 6 post-treatment)
- Requires another treatment less than 12 weeks from the last injection
- Reaches Week 52

Refer to the SOA (Table 1) for EOS activities.

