8.1.3 VARIATION FROM SCHEDULED VISIT DAYS

To allow for scheduling flexibility, limited variation will be permitted from the specified time of each visit (Table 3).

Table 3. Allowed Variation from Scheduled Visit Days

Scheduled Visit After Each Treatment	Allowed Variation (calendar days)
Weeks 4 and 6	± 3 days
Weeks 12, 16, 20, 24, 28, 32, 36, 40, 44, 48, and 52/EOS	± 6 days
Treatment #2, #3, and #4	± 14 days

Note: Two weeks after each Treatment (at Week 2 [allowed variation: ± 3 days]), the subject will be contacted by telephone to follow up on clinical effect, any AEs or changes in concomitant medications.

A subject who experiences significant recurrence of CD symptoms (e.g. pain) during the study before his/her TWSTRS-total score reaches the target TWSTRS score may request another treatment before the next scheduled visit. In this case, the subject may have an unscheduled visit for the investigator to assess whether another treatment is warranted based on the subject's symptoms and neurologic exam findings. If the investigator confirms that retreatment is clinically indicated, the subject may receive another treatment at this visit, unless less than 12 weeks have passed since the last injection or the injection will occur after Week 40 (i.e., there is less than 12 weeks of follow up left in the 52-week study period).

Note: After each Treatment, study visits are reset to begin from that Treatment to Week 4, Week 6, Week 12, and every 4 weeks thereafter.

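### Median duration of effect and its 95% CI are assigned to the log-rank test, which gives neither, and no within-subject adjustment is named if treatment cycles are pooled

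*Protocol*

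**What the plan says.** Protocol 9.6 (Planned Analyses) sets the endpoint as "Duration of effect after each treatment, defined as time (number of weeks) from treatment until loss of 80% of the peak treatment effect", with the peak taken from Weeks 4 and 6. On display it says "Kaplan-Meier survival curves will be plotted for each dose level for the time-to-event endpoints". On estimation it says "Point estimate of median duration and 2-sided, 95% confidence intervals (CIs), will be generated using the log-rank test". The next sentence concedes that "A subject might be counted more than once or in multiple groups due to multiple injections cycle", and the section then allows exploratory comparisons between subgroups. It mentions no clustered variance, bootstrap or one-record-per-subject rule.

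On the unit of summary the visible texts differ. Protocol 9.6 and SAP 6.1 allow efficacy endpoints to be summarised by dose, by cycle, or by both. SAP Section 8 says by dose and by cycle together. All three add an exception for anything specified otherwise. The detailed efficacy text that follows in SAP Section 8 is not shown. The visible part of SAP Section 10 drops the intent-to-treat and per-protocol populations and multiple imputation, adds COVID-19 analyses, and does not mention duration of effect.

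**The concern.** There are two separate problems.

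First, the named method does not produce the named quantities, so whoever programs the analysis must choose an interval method that the protocol does not record.

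Second, a curve per dose level on which a subject can be counted more than once reads most naturally as a curve pooled over cycles. On a dose-by-cycle curve each subject appears once. The default Kaplan-Meier variance treats every record as independent. Repeated durations in one patient are plausibly correlated, and the interval would then be too narrow. Subjects with shorter effects can also fit more cycles into 52 weeks, so a pooled median may answer a different question from a median over subjects. In an exploratory log-rank comparison of doses, the same subject could sit on both sides.

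What is at stake is the reported precision, and to a lesser extent the location, of the median duration after repeat treatment.

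**Working it through.** **The plan's own figure.** There is none to reproduce. The documents give no expected median, event count or power for this endpoint. The figure of about 350 subjects (Protocol 9.1, SAP 3.6) is an exposure requirement.

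**Inputs from the documents.**
- Cycles: "up to four continuous treatment cycles of DAXI for injection at doses of 125 U, 200 U, 250 U, and 300 U" (SAP 3.4).
- Retreatment after an unscheduled visit is allowed "unless less than 12 weeks have passed since the last injection or the injection will occur after Week 40" (Protocol 8.1.3), within a 52-week study.
- An end-of-study visit may occur when the subject "Requires another treatment less than 12 weeks from the last injection" (Protocol 8.1.2.4). Protocol 7.2 is also permissive.
- Zero durations: "If a subject discontinues or withdraws from the study prior or at Week 6, his/her duration of effect will be set to 0" (Protocol 9.6). The same applies when there is no reduction at Weeks 4 and 6.

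**Assumed inputs, not in the documents.** Log-normal durations with median 16, 20 or 24 weeks and log-scale SD 0.45; intraclass correlation (ICC) 0 to 0.7; 350/4 = 87.5, so 88 subjects per dose; the same dose in every cycle.

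**Step 1: cycles against duration.** If a subject has constant duration d of at least 12 weeks and is retreated when the effect is lost, injection k falls at week (k-1)d and must not come after Week 40. Four cycles need 3d ≤ 40, so d ≤ 13.3. Three need 2d ≤ 40, so d ≤ 20. Two need d ≤ 40. Shorter responders who stay therefore contribute more records.

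**Step 2: interval width by design effect.** The SE ratio is √(1+(m-1)·ICC) for m cycles per subject. With m = 2 and ICC 0.3 it is √1.3 = 1.14. With m = 3 and ICC 0.7 it is √2.4 = 1.55. This formula is for a mean, so it is only a rough guide for a median.

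**Step 3: simulation of pooled cycles.** The runs used at most four cycles at least 12 weeks apart, none after Week 40, with follow-up ending at Week 52. Subjects with effect under 12 weeks stay and are retreated at 12 weeks. The interval is Brookmeyer-Crowley (log-log), taking records as independent. There were 600 runs per row; large-sample medians came from 40,000 subjects. Width needed is 3.92 times the SD of the median across runs.

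| Median (weeks) | ICC | Cycles per subject | Coverage of pooled median | Mean width / width needed | Pooled minus cycle-1 median (weeks) |
|---|---|---|---|---|---|
| 16 | 0 | 2.76 | 94.3% | 2.33 / 2.41 | -0.05 |
| 16 | 0.3 | 2.84 | 88.7% | 2.19 / 2.69 | -0.59 |
| 16 | 0.5 | 2.88 | 87.7% | 2.10 / 2.59 | -0.98 |
| 16 | 0.7 | 2.92 | 83.5% | 2.02 / 2.92 | -1.36 |
| 20 | 0 | 2.38 | 94.7% | 3.21 / 3.14 | -0.08 |
| 20 | 0.3 | 2.45 | 91.3% | 3.02 / 3.48 | -0.82 |
| 20 | 0.5 | 2.49 | 89.2% | 2.90 / 3.63 | -1.35 |
| 20 | 0.7 | 2.54 | 86.2% | 2.75 / 3.69 | -1.89 |
| 24 | 0 | 2.11 | 95.7% | 4.28 / 4.13 | +0.03 |
| 24 | 0.3 | 2.16 | 89.5% | 3.99 / 4.67 | -1.02 |
| 24 | 0.5 | 2.20 | 88.7% | 3.79 / 4.56 | -1.56 |
| 24 | 0.7 | 2.25 | 86.8% | 3.60 / 4.58 | -2.47 |

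The Monte Carlo SE is √(0.95×0.05/600) = 0.9 percentage points at 95% coverage and about 1.5 at 85%. As a cross-check at median 20 and ICC 0.5, the simulated ratio is 3.63/2.90 = 1.25, against √(1+1.49×0.5) = 1.32 from the formula. The default interval there is 1 - 2.90/3.63 = 20% too narrow. The cycle-1 curve, with one record per subject, covered 93% to 96% in all 12 settings.

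**Step 4: what happens when short responders leave.**
- Exit when the effect lasts under 12 weeks, plus 5% or 15% zero-duration cycles that end participation (median 20, ICC 0.3 or 0.5): median shift -0.04 to -0.13 weeks; pooled coverage 91% to 94%, against 92% to 94% for cycle 1 alone.
- Exit without zero durations, between-subject SD 0.35 to 0.45 and within-subject SD 0.25: shift +0.7 to +0.9 weeks at median 16, -0.2 to -0.3 at 20, and -1.1 to -1.7 at 24.

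**Step 5: durations read only at visits** (12, 16, 20 weeks and so on; one setting, median 20, ICC 0.5). The median did not shift and pooled coverage was 99.8%. Estimates then move in 4-week steps and the assumed median is itself a visit week, so coverage says little about width. The table applies to durations treated as continuous.

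**The case against.** The strongest reply is that the log-rank wording is a slip. Kaplan-Meier curves are named in the sentence before, and standard Kaplan-Meier output includes a median with an interval, so no analyst would be blocked. That is fair as to consequence, but the sentence is complete, wrong, and leaves the interval method open.

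The second reply is that treating cycles as independent is nowhere stated. SAP Section 8 summarises by dose and cycle, which would put each subject on each curve once and remove both the correlation and the selection problem. The detailed SAP text is hidden and may settle it. This stands as a real possibility. It is not confirmed: SAP 6.1 keeps the looser wording, all versions allow exceptions, and Protocol 9.6 specifies dose-level curves with repeat counting.

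Three stronger readings are tempting, and the documents do not support them.
- A reader might infer that the pooled median is necessarily pulled toward short responders. That depends on whether subjects needing treatment before 12 weeks stay or leave. Protocol 7.2 and 8.1.2.4 say only that they may be withdrawn, and the simulated shift changes sign.
- A reader might infer that coverage collapses. With 150 subjects per dose, simulated coverage of the median over subjects is 5% to 21%. But 4×150 = 600 is well above 350, the SDs used imply an ICC of 0.66 to 0.76, and Protocol 9.6 defines duration after each treatment, not per subject.
- A reader might take duration as the main efficacy claim. The visible text never says so. The primary endpoints are safety and immunogenicity (Protocol 9.3, SAP 4.1).

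**Conclusion.** The point holds in limited form. The estimation sentence in Protocol 9.6 is wrong on its face, with no assumption needed. The under-stated uncertainty is conditional on three things: that cycles are pooled, that the default variance is used, and that durations within a subject are positively correlated.

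Under those conditions, with continuous durations and about 88 subjects per dose, coverage falls to about 89-91%, 88-89% and 84-87% at ICC 0.3, 0.5 and 0.7. At ICC 0 the interval is correct. The pooled median may differ from the cycle-1 median by about -2.5 to +0.9 weeks, with size and sign set by who is retreated; in some plausible settings the difference is close to zero. The documents give no ICC, spread or subjects per dose, so these are ranges under assumptions and not predictions.

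The analysis is descriptive and the between-group comparisons are exploratory. No primary safety or immunogenicity conclusion rests on it. It should be fixed before the analysis is run, but it does not threaten the trial's main purpose.

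**What to change.** Replace the estimation sentence with:

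> Median duration will be estimated by Kaplan-Meier with a Brookmeyer-Crowley (log-log) 95% CI, by dose within each treatment cycle, each subject contributing once per curve.

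If a curve pooled over cycles is also wanted, label it as a per-injection summary and give it a subject-level bootstrap or cluster-robust interval. That repairs the width; it does not turn the per-injection median into a median over subjects, which is why the label matters. Keep exploratory log-rank comparisons within a single cycle, or use a subject-clustered variance. Record the change in SAP Section 10, and make SAP 6.1 and Section 8 agree on the unit of summary. If the hidden SAP text already does this, only the protocol sentence needs to be marked as superseded.

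The cost is wording and standard code, with no new data. The downside is that pooled intervals become wider, with an SE roughly 1.1 to 1.55 times the default under the assumed correlations. Dose-by-cycle curves will also rest on fewer subjects in later cycles.
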